4.4 Secondary Endpoints

The following secondary endpoints will be evaluated in the study, but there are no formal hypotheses that are tested or associated significance levels assigned to results. Nominal confidence intervals may be calculated in summarizing clinical results for secondary endpoints but not for purposes of product labeling.

1. Acute device success will be summarized by the success rate and associated 95% confidence interval.
2. Primary Unassisted Patency at 6 Months will be summarized by the patency rate and associated 95% confidence interval.
3. Time-to-First-Cannulation will be summarized by the median time and frequency distribution.
4. Number and type of interventions required to maintain secondary patency will be summarized by the frequency distributions of numbers and types of interventions.
5. Number and type of serious adverse events (SAEs) will be summarized by frequency distributions of the numbers and types of SAEs, the subject rates of SAEs by type, and the proportion of subjects with at least one SAE.

4.5 Additional Safety Data

In addition to summarizing and reporting SAEs (Secondary Endpoint 6), the number and type of non-serious adverse events (AEs) will be summarized by frequency distributions of the numbers and types of AEs and the subject rates of AEs by type.

4.6 Interim Analysis

No interim analysis is planned for the current InterGraft VIG study.

4.7 Gender Analysis

Cumulative patency rates between genders will be compared by gender using a log rank test statistic to compare their respective Kaplan-Meier survival curves. The heterogeneity of cumulative patency rates will also be examined using the test statistic used for the primary endpoint analysis. Gender specific summary statistics will also be provided for study primary and secondary endpoints.

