2.2 Study Endpoints and Hypotheses

2.2.1 Primary Endpoint

The primary endpoint is cumulative patency at 6 months, defined as the percentage of subjects free from loss of access of the study graft for hemodialysis, assessed at 6 months.

The primary study endpoint of the cumulative patency rate at 6 months will be evaluated in the following testable hypotheses:

$$H_0: (\text{Cumulative Patency Rate})_{6 \text{ Months}} \leq \text{PG}$$

$$H_1: (\text{Cumulative Patency Rate})_{6 \text{ Months}} > \text{PG}$$

Where, PG = Performance Goal, here equal to 75%.

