2.3 Sample Size Justification

The required sample size for the study was estimated using the following assumptions:

- Test basis: Kaplan-Meier estimate of cumulative patency rate at 6 months, with exact binomial estimation for purposes of sample size
- Type I error (alpha): 0.025 (one-sided)
- Statistical power: 80%
- Performance Goal (PG): 75%
- Expected cumulative patency for InterGraft at 6 months: 84.6%.

Based on the above assumptions, a total of 146 evaluable subjects would be required to compare observed cumulative patency to a PG of 75%. With an expected loss-to-follow-up rate of 8% over 6 months, a total of 158 subjects would need to be enrolled in the evaluation phase.

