4.3 Primary Endpoint

Cumulative patency at 6 months will be evaluated using the estimated patency from a Kaplan Meier survival analysis. The test statistic will take the following form:

$$\text{Z-test statistic} = (P - 0.75) / \text{SE}(P)$$

Where, (P) represents the Kaplan Meier estimate of cumulative patency at 6 months, and the standard error SE (P) is estimated using the method of Peto *et al* (1977).

Subjects who withdrawn for reasons other than loss of cumulative patency will be included in the analysis up until the time of withdrawal, and be considered censored in the analysis, according to usual convention, after withdrawal.

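### The second gender check, on heterogeneity of 6-month patency, uses a one-sample statistic against 75% that contains no comparison of men with women

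*SAP*

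**What the plan says.** SAP 4.7 has three parts on gender, and the Gender Analysis paragraph of Protocol 18.0 has the same text.

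- A comparison of the curves: "Cumulative patency rates between genders will be compared by gender using a log rank test statistic to compare their respective Kaplan-Meier survival curves".
- A second check, on the rates: "The heterogeneity of cumulative patency rates will also be examined using the test statistic used for the primary endpoint analysis".
- Gender-specific summaries of the primary and secondary endpoints.

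SAP 4.3 and Protocol 18.0 (Primary Endpoint) define the primary statistic as Z = (P - 0.75)/SE(P). Here P is a single 6-month Kaplan-Meier estimate; on its precision the text says "the standard error SE (P) is estimated using the method of Peto" and co-authors (1977). The constant is the performance goal set in SAP 2.2.1: "Where, PG = Performance Goal, here equal to 75"%. Neither document gives a two-group form of this statistic, a standard error for a difference, or a criterion for gender heterogeneity.

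**The concern.** Heterogeneity between genders is a question about P_men - P_women. The named statistic answers a different one: whether a single rate exceeds 75%. Run within each gender, it shows whether each gender clears the goal. Whether a gender clears depends on its size as well as its rate, so a smaller group can fail at the same rate at which a larger one passes. Conversely, both can clear the goal when their rates differ. Run on the pooled sample, it carries no information on gender at all.

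The log-rank test will still give a valid between-gender p-value. It compares whole curves, however, and gives no 6-month difference or confidence interval. The 6-month rate is the primary endpoint, and the second check appears intended for it. If the sentence is left as it is, someone will have to decide what it means after the data are in.

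**Working it through.** **Inputs from the documents.** Performance goal 75% (SAP 2.2.1). One-sided alpha 0.025, power 80%, expected patency 84.6%, 146 evaluable, 8% loss to follow-up, 158 enrolled (SAP 2.3). The pass mark is therefore Z > 1.96.

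**Assumptions, not in the documents.** Gender splits of 73/73, 88/58 and 100/46, with 117/29 as an extreme. Also, one gender passing and the other failing is read as heterogeneity.

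**1. The plan's own figure.** An exact one-sample binomial test with n = 146 succeeds at 120 or more patent, with one-sided alpha 0.0249 and power 82.3% at 84.6%. The one-sample normal approximation gives n = 145. With 8% added, 146 × 1.08 = 157.7, or 158. The plan's 146 is thus reproduced as a one-sample design against a constant.

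**2. Standard error.** In its usual form the Peto SE is P·sqrt((1 - P)/r), with r the number at risk at 6 months. Without censoring r = nP, so SE(P) = sqrt(P(1 - P)/n).

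**3. The statistic against the contrast** Z_d = (P_men - P_women)/sqrt(SE_men² + SE_women²):

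| Men | Women | Z men | Z women | Z_d |
|---|---|---|---|---|
| 85/100 (85.0%) | 39/46 (84.8%) | 2.80 | 1.85 | 0.03 |
| 70/73 (95.9%) | 61/73 (83.6%) | 8.99 | 1.97 | 2.51 |
| 90% of 73 | 60% of 73 | 4.27 | -2.62 | 4.46 |

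- First row: (0.850 - 0.75)/0.0357 = 2.80 and (0.848 - 0.75)/0.0530 = 1.85. Almost identical rates give one pass and one failure.
- Second row: (0.959 - 0.75)/0.0232 = 8.99 and (0.836 - 0.75)/0.0434 = 1.97. Both pass, although Z_d = 0.1233/sqrt(0.0232² + 0.0434²) = 2.51.
- Third row: the pooled rate is exactly 75%, so the pooled Z is 0.00 despite a 30-point difference.

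**4. How often the two verdicts disagree when the true rates are equal.** With A and B the two exact pass probabilities, the discordance is A(1 - B) + B(1 - A). The smallest passing counts are 61/73, 73/88, 49/58, 83/100 and 40/46. At 84.6% the pass probabilities are 0.670 (n = 73), 0.725 (88), 0.597 (58), 0.727 (100) and 0.424 (46). For 100/46 this gives 0.727 × 0.576 + 0.424 × 0.273 = 0.53.

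| True rate, both genders | 73/73 | 88/58 | 100/46 |
|---|---|---|---|
| 75% | 0.105 | 0.104 | 0.073 |
| 80% | 0.400 | 0.398 | 0.344 |
| 84.6% | 0.442 | 0.456 | 0.535 |
| 90% | 0.055 | 0.072 | 0.178 |
| 95% | 0.000 | 0.001 | 0.008 |

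A simulation with censoring gives a similar picture. It used 20,000 runs, 158 enrolled, exponential loss of patency, 8% exponential loss to follow-up and Peto SEs, with splits 79/79, 95/63 and 108/50. Discordance was 0.475, 0.483 and 0.504 at 84.6%, and 0.075, 0.095 and 0.136 at 90%.

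**5. The opposite error.** With true rates of 97% and 88% (73/73), both genders pass with probability 0.91. The two-sample contrast would detect that difference with probability 0.60.

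**6. Size of the contrast** (nominal 5%, two-sided, exact, no censoring):

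| True rate, both genders | 73/73 | 88/58 | 100/46 | 117/29 |
|---|---|---|---|---|
| 84.6% | 5.1% | 5.1% | 6.1% | 7.7% |
| 95% | 6.4% | 5.8% | 8.5% | 19.5% |

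In the censored simulation it was 4.9%, 4.9% and 5.3% at 84.6%, and 4.6%, 5.4% and 5.6% at 90%.

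**The case against.** The strongest reply concerns weight. The plan already has a valid log-rank test and gender-specific summaries, so the reader gets a between-gender p-value and both 6-month estimates and can subtract one from the other. This stands. What is missing is a stated standard error, confidence interval and test for that difference.

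Second, the discordance probabilities depend on a pass/fail reading that the plan does not contain. It says only that heterogeneity will be examined, whereas SAP 4.8 sets a 0.15 threshold for sites. This also stands: the figures illustrate a likely misreading and are not error rates of a planned decision. The 84.6% row is also the highest of the rates tabulated.

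Third, the authors may have meant the same kind of statistic, a Z on 6-month Kaplan-Meier estimates with Peto standard errors, applied to the gender difference. That is plausible, but neither document says so, and the statistic they point to has 0.75 in its numerator. If it was the intention, the fix below only writes it down.

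Fourth, the replacement has limits. Its size is inflated in uneven splits at high patency. If every subject in one gender stays patent, that gender's standard error is zero. In a group of 29 without censoring this has probability 0.95^29 = 0.23 at 95% and 0.846^29 = 0.008 at 84.6%. This calls for a nominal label but gives no reason to keep the present sentence.

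**Conclusion.** The concern holds. As written, the second gender check uses a statistic that cannot measure a difference between genders, and this follows from the definitions alone. The practical effect can be sized only under assumptions. If opposite verdicts are read as heterogeneity, equal true rates of 84.6% would produce them with probability 0.44 to 0.53 over the three main splits, against 0.07 to 0.10 at 75%, 0.34 to 0.40 at 80%, 0.05 to 0.18 at 90% and below 0.01 at 95%.

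The consequence is limited to a supportive analysis. The log-rank test, the gender summaries, the primary test, its alpha and the 146 evaluable subjects are untouched. The sentence should be corrected before the data are analysed, but no study conclusion depends on it.

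**What to change.** In SAP 4.7 and in Protocol 18.0 (Gender Analysis), replace the heterogeneity sentence with:

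> The difference in 6-month Kaplan-Meier cumulative patency between genders will be tested with Z = (P_men - P_women)/sqrt(SE_men² + SE_women²), using the same SE method as the primary analysis, and reported with its two-sided 95% confidence interval and a nominal p-value.

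Keep the log-rank test and the gender-specific summaries. If Z values against 75% are wanted by gender, report them as descriptive and do not call them heterogeneity. If one gender has no loss of patency, say so in the report and rely on the log-rank test and the summaries, because the normal approximation is then unreliable.

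The cost is one sentence in each document. No new data are needed, and the primary analysis, its SE method and the sample size do not change. The drawback is the inflated size in very uneven splits or at very high patency, which is why the p-value is labelled nominal.

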4.8 Pooling of Sites

Cumulative patency rates will be compared between study sites using a Chi-square test to evaluate the association between rates and sites. A p-value of 0.15 or less would be considered evidence of a possible site interaction, requiring a further evaluation of subject baseline factors to determine if site differences can be explained by these factors.

4.9 Sensitivity Analyses

The primary endpoint is cumulative patency at 6 months, defined as the percentage of subjects free from loss of access of the study graft for hemodialysis, assessed at 6 months. Loss of access, including graft abandonment, and the associated time of occurrence will be considered events for purposes of the primary endpoint analysis.

Subjects who have died for reasons unrelated to the study device will be considered as censored with regard to the primary endpoint analysis at the time of death, and their last known status will be used.

Subjects who have become lost to follow-up or who have withdrawn consent for participation in the study prior to 6 months will be considered to have missing primary endpoint outcomes. In the primary analysis, these subjects will be considered to have been censored at the last documented determination of their status prior to study exit. Sensitivity analyses will also be performed to determine the potential impact of these missing data on the primary analysis results, including a tipping point analysis where their status at the time of study exit is assumed to be loss of patency.

4.10 Protocol Violations

All protocol violations will be summarized and reported by type of violation and classification as major or non-major violation.

4.11 Data Collection and Management

4.11.1 Data Collection

Primary data collection based on source documented medical records will be performed by study coordinators or other designated research staff at each site. Electronic data capture will be used. Site training (web-based) will be provided by the Data Coordinating Center (DCC). All EDC training will be documented in the Investigator site file. Throughout the study, a help desk at the DCC will be available for any questions that arise from sites concerning the EDC.

4.11.2 Data Management

The DCC will use a validated clinical data management system consisting of a relational database and a web application to capture the study data through single-pass data entry. Automated edit checks for missing, discrepant, and out of range data will be programmed into the data entry forms, and manual edits will be conducted by the DCC Managers on an ongoing basis. The Sponsor will provide a list of edit checks to the DCC.

Any data discrepancies identified during data monitoring will be communicated to study sites for resolution or justification. Once all discrepancies and queries have been resolved, the site principal Investigator will confirm the data accuracy with his/her signature on a Verification CRF. Once the study is completed, all data have been entered into the clinical database, and all discrepancies have been resolved, an audit will be conducted to verify that all requirements for database lock have been met. After database lock, the DCC will export the data into SAS datasets and provide them to the project statistician.

CRF submission status will be tracked by the DCC.

